6.3. Permanent Discontinuation from Study Treatment

Subjects will receive study treatment until disease progression, death or unacceptable toxicity, including meeting stopping criteria for significant toxicity as outlined in Section 3.10 and other relevant safety management guidelines outlined in the protocol, or until a maximum of 16 treatment cycles. In addition, study treatment may be permanently discontinued for any of the following reasons:

- deviation(s) from the protocol
- request of the subject or proxy (withdrawal of consent by subject or proxy)
- investigator's discretion
- a dose delay of >14 days unless the investigator or GSK Medical Monitor agree that subject derives benefit and that further treatment benefits will outweigh the risks. Exceptions apply to nephrotoxicity as outlined in Section 3.10.2
- intercurrent illness that prevents further administration of study treatment(s)
- subject is lost to follow-up
- study is closed or terminated
- subject completes maximum number of treatment cycles per protocol
- The primary reason study treatment was permanently discontinued must be documented in the subject's medical records and electronic case report form (eCRF)

If the subject voluntarily discontinues from treatment due to toxicity, 'adverse event (AE)' will be recorded as the primary reason for permanent discontinuation on the eCRF.

Once a subject has permanently discontinued from study treatment, the subject will not be allowed to be retreated.

All subjects who discontinue from study treatment will have safety assessments at the time of discontinuation and during post-study treatment follow-up as specified in Time and Events Tables (see Section 7.1).

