13.7.7. Clinical Activity Analyses

Overall Response Rate (ORR) is one of the secondary endpoints to measure clinical activity of this study.

For multiple myeloma, ORR is defined as the percentage of subjects with a confirmed PR or better (i.e. PR, VGPR, CR and sCR), according to the IMWG Panel I ([Appendix 1](#)), as assessed by the investigator. In addition, Clinical Benefit rate (CBR) is defined as the percentage of subjects with a confirmed MR or better (i.e. MR, PR, VGPR, CR and sCR), according to the IMWG Panel I ([Appendix 1](#)), as assessed by the investigator.

The number and percentage of subjects in the following response categories will be presented sCR (stringent complete response), (complete response) CR, (very good partial response) VGPR, (partial response) PR, (minimal response) MR, stable disease (SD), progressive disease (PD), and not evaluable (NE)

sCR+CR+VGPR+PR for overall response (ORR)

sCR+CR+VGPR+PR+MR for Clinical Benefit rate (CBR)

The corresponding exact 95% CI for ORR and Clinical Benefit Rate (CBR) will also be provided. Subjects with unknown or missing response will be treated as non-responders, i.e., these subjects will be included in the denominator when calculating percentages of response.

For lymphoma, ORR is defined as the percentage of subjects with confirmed CR, or PR, as described in the Revised Response Criteria for Malignant Lymphoma ([Appendix 2](#)). ORR for lymphomas will be summarized in a similar way as multiple myeloma. The corresponding exact 95% CI for ORR will also be provided.

Other exploratory time-to-event (TTE) endpoints related to clinical activity for Part 2 (MM) of this study are TTP, DOR, TTR, and PFS.

Time to disease progression (TTP) is defined as the time from first dose until the earliest date of PD per IMWG, or death due to PD. Determination of dates of TTP event and dates for censoring will be described in the RAP. **Duration of response (DOR)** is defined as the time from first documented evidence of PR or better until disease progression (PD) per IMWG, or death due to PD among subjects who achieve a response

(i.e. confirmed PR or better). Responders without disease progression will be censored at the censoring time point for TTP.

Time to response (TTR) is defined as the time between the date of first dose and the first documented evidence of response (PR or better). Subjects without confirmed response (PR or better) will be censored at the censoring date for TTP.

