Progression-free survival (PFS) is defined as the time from first dose until the earliest date of disease progression (PD) per IMWG, or death due to any cause. Determination of dates of PFS event and dates for censoring will be described in the RAP.

For all the TTE endpoints described above, median TTE with 95% CI will be estimated employing the Kaplan-Meier method as data permits. A Kaplan-Meier survival curve will be generated. The number and percentage of subjects who had the event or were censored will also be reported.

Exploratory subgroup analyses may be performed for all endpoints to measure clinical activity as appropriate.

Overall Survival: The protocol is amended to collect long-term survival data (i.e. up to 1 year after last subject completes or discontinues treatment). Subjects who have already completed the study will be contacted to request re-consent.

If all the patients (who were alive at the time of study completion) can be re-consented, OS landmark analysis may be performed at 9 and 12 months using Kaplan-Meier analysis as data permits.

Otherwise, only descriptive analysis (number and % of deaths and lost to follow-up) will be performed.

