	
 • Only in patients without measurable serum and urine M-protein levels; the difference between involved and uninvolved FLC levels. The absolute increase must be > 10 mg/dL • Bone marrow plasma cell percentage; the absolute percentage must be $\geq 10\%$⁷ • Definite development of new bone lesions or soft tissue plasmacytomas or definite increase in the size of existing bone lesions or soft tissue plasmacytomas • Development of hypercalcaemia (corrected serum calcium > 11.5 mg/dL or 2.65mmol/L) that can be attributed solely to the plasma cell proliferative disorder
Relapse	
Clinical relapse requires one or more of:
 
 • Direct indicators of increasing disease and/or end organ dysfunction (CRAB features).⁶ It is not used in calculation of time to progression or progression-free survival but is listed here as something that can be reported optionally or for use in clinical practice • Development of new soft tissue plasmacytomas or bone lesions • Definite increase in the size of existing plasmacytomas or bone lesions. A definite increase is defined as a 50% (and at least 1 cm) increase as measured serially by the sum of the products of the cross-diameters of the measurable lesion • Hypercalcemia (> 11.5 mg/dL) [2.65 mmol/L] • Decrease in haemoglobin of ≥ 2 g/dL [1.25 mmol/L] • Rise in serum creatinine by 2 mg/dL or more [177 mol/L or more]
Relapse from CR⁵ (to be used only if the endpoint studied is DFS)⁸	
Any one or more of the following:
 
 • Reappearance of serum or urine M-protein by immunofixation or electrophoresis • Development of $\geq 5\%$ plasma cells in the bone marrow⁷ • Appearance of any other sign of progression (i.e., new plasmacytoma, lytic bone lesion, or hypercalcaemia)

Overall Responders: PR, VGPR, CR, sCR

Clinical Benefit Rate: Overall responders + MR

Adapted from Durie BGM, et al. Leukemia 2006; 20: 1467-1473; and Kyle RA, Rajkumar SV. Leukemia 2008;23:3-9.

Note: A clarification to IMWG criteria for coding CR and VGPR in patients in whom the only measurable disease is by serum FLC levels: CR in such patients is defined as a normal FLC ratio of 0.26–1.65 in addition to CR criteria listed above. VGPR in such patients is defined as a >90% decrease in the difference between involved and uninvolved free light chain (FLC) levels.
 3 Confirmation with repeat bone marrow biopsy not needed.

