Updated with current template language which allows for analyses of genetic variants with disease susceptibility, severity, and progression of disease.

16.11.5. Amendment 5

Amendment 5 applies to all sites in Canada, United Kingdom, and United States

The protocol Amendment 4 dated 05 May 2016 (applied to all sites) is replaced by Amendment 5 with the effective date of DD MMM YYYY.

Summary of Changes

The following protocol changes have been implemented to include additional follow up of multiple myeloma subjects for ocular exams (for those whose corneal signs or symptoms have not resolved), additional patient reported outcome instruments, addition of time-to-event endpoints as exploratory objectives. Subjects who have completed treatment or the 3 month follow up visit (end of study) prior to amendment 5 will be reconsented for further follow up and survival status. Other administrative changes are also included

Original text displayed as strikethrough indicates replaced or removed text. New text is displayed as underline. Revisions within tables is either presented with the entire table or displayed as text (i.e., for larger tables). Typos or minor word changes are not presented.

List of Changes

1. List of Abbreviations

CI	Confidence interval
DOR	Duration of response
NEI-VFQ-25	National Eye Institute Visual Functioning Questionnaire - 25
OSDI	Ocular Surface Disease Index
PFS	Progression-free survival
SD	Stable disease
TTP	Time to progression

Rationale for Change: Updated to include new abbreviations used within the amendment.

2. Protocol Synopsis

STUDY OBJECTIVES, ENDPOINTS AND HYPOTHESES

Objective	Endpoint
Exploratory	

 To explore the effect of GSK2857916 on bone pain symptoms (including bone pain, fatigue and visual symptoms) and impacts on and HRQoL in subjects with relapsed/refractory MM (Part 2) 	
 Changes from baseline in bone pain/fatigue and analgesic use as measured by the eDiary Interviews with subjects to further characterize changes in bone pain symptoms (including bone pain, fatigue and visual symptoms) and impacts on HRQoL

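### The hypercalcaemia criterion for progressive disease pairs 11.5 mg/dL with 2.65 mmol/L, which are different calcium levels, so a corrected calcium between them has no settled classification

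*Protocol*

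**What the plan says.** Protocol Appendix 1 (Section 16.1) sets out the myeloma response criteria. Its Progressive Disease row includes "Development of hypercalcaemia (corrected serum calcium > 11.5 mg/dL or 2.65mmol/L) that can be attributed solely to the plasma cell proliferative disorder". The Relapse row repeats the pair with the SI figure in brackets: "Hypercalcemia (> 11.5 mg/dL) [2.65 mmol/L". Footnote 5 to the table asks for two assessments in a row before relapse or progression is classified. Both that footnote and the Relapse row itself keep the relapse definitions out of the calculation of TTP and PFS.

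The PD definition is used in two places:

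- **Endpoints (Section 13.7.7).** PFS is "the time from first dose until the earliest date of disease progression (PD) per IMWG, or death due to any cause". TTP "is defined as the time from first dose until the earliest date of PD per IMWG, or death due to PD". DOR likewise ends at PD or death due to PD. Section 2 lists all three as exploratory, for the Part 2 myeloma cohort.
- **Treatment (Section 6.3).** "Subjects will receive study treatment until disease progression, death or unacceptable toxicity". The same section does not allow retreatment after permanent discontinuation.

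Calcium and albumin are both in the chemistry panel (Table 15), with no unit given. On the three-weekly expansion schedule (Section 7.1.2.1), chemistry is drawn at screening, on Days 1, 8 and 15 of Cycle 1, at the start of each later cycle and at the end of treatment. Section 13.7.7 makes response investigator-assessed. On countries, the amendment appendix states: "Amendment 5 applies to all sites in Canada, United Kingdom, and United States".

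**The concern.** The PD row offers the two calcium figures as one cut-off, and the bracket in the Relapse row shows that the SI figure is meant as the conversion of the conventional one. If they do not convert, the criterion has two thresholds. An investigator working from the printed table could call PD, or not, on the same calcium.

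At stake are the dating of PD events in TTP, DOR and PFS and, for the individual subject, a treatment stop that cannot be reversed. Calcium is measured often enough for the criterion to be applied throughout treatment.

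**Working it through.** **Inputs.** 11.5 mg/dL and 2.65 mmol/L come from Appendix 1. The molar mass of calcium is a physical constant that the protocol does not give. It is taken as 40.078 g/mol, with 40.0 to 40.1 tried as a range.

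**Formula.** mmol/L = (mg/dL × 10) / molar mass.

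**Does the plan's pair reproduce?** No.

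- 11.5 × 10 / 40.078 = 2.87 mmol/L (2.868 to 2.875 over the range). Printed: 2.65.
- 2.65 × 40.078 / 10 = 10.62 mg/dL (10.60 to 10.63 over the range). Printed: 11.5.
- The pair would need a molar mass of 115 / 2.65 = 43.4 g/mol, so rounding does not explain it.
- Nor does a switch to milliequivalents: 2 × 2.869 = 5.74 mEq/L.

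**Size of the gap.** 2.869 − 2.65 = 0.22 mmol/L. 11.5 − 10.62 = 0.88 mg/dL. 2.869 / 2.65 = 1.083, so the conventional figure is about 8% above the SI figure.

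**Control: the other bracketed conversions in the Relapse row.**

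- "Decrease in haemoglobin of ≥ 2 g/dL [1.25 mmol/L": 20 g/L / 16.114 g/mmol (haemoglobin per iron-bearing subunit, an assumed constant) = 1.24 mmol/L. This agrees with the printed figure to rounding.
- "Rise in serum creatinine by 2 mg/dL or more [177 mol/L or more": 2 × 88.4 (the factor in Appendix 9) = 176.8. The number agrees; the unit is misprinted and should be µmol/L.

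Of the three pairs, calcium is the only one whose numbers disagree.

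**What happens in the band.** Take a corrected calcium of 2.75 mmol/L. It equals 2.75 × 4.0078 = 11.02 mg/dL. It is above 2.65 mmol/L and below 11.5 mg/dL.

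| Reading of the PD row | Is 2.75 mmol/L (11.02 mg/dL) above the cut-off? |
|---|---|
| SI figure applied | Yes |
| Conventional figure applied | No |
| 'Or' read literally, either figure suffices | Yes, at every site; 11.5 mg/dL then has no effect |

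The readings disagree for any value between 2.65 and 2.87 mmol/L and agree outside that band.

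**The case against.** The strongest reply is that the mismatch will seldom decide anything. The hypercalcaemia must arise on study, be due to the myeloma alone, be confirmed on two assessments in a row, and come before any progression by M-protein, light chains, marrow, bone lesion or plasmacytoma. The endpoints it touches are exploratory, in a single-arm cohort, and summarised by Kaplan-Meier as data permit. The futility rule counts responses. The Relapse row feeds neither TTP nor PFS, so correcting it there is only for consistency. All of this stands. It limits how often the conflict matters but does not make the two figures equal, and a repeat measurement does not help when the cut-off itself is ambiguous.

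Two stronger readings are tempting, and the protocol does not support either:

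- A reader might infer that sites reporting in mmol/L do declare progression earlier than sites reporting in mg/dL. The protocol names three countries but never says which sites report in which unit. On the literal reading of 'or', the lower figure applies everywhere and no site difference arises.
- A reader might infer that, because Table 14 sets no calcium limit, subjects could enter already meeting the criterion. The PD row requires that hypercalcaemia develop, and a subject already in the band at entry has not plainly developed it on study.

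Appendix 1 is described as adapted from published criteria. Whether the pair was carried over or introduced here cannot be told from the protocol, but the printed table is what investigators apply.

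**Conclusion.** The point holds as an arithmetic contradiction in a decision threshold: the two printed cut-offs differ by 0.22 mmol/L (0.88 mg/dL), whichever plausible molar mass is used. For a corrected calcium between 2.65 and 2.87 mmol/L that meets the other conditions and is the sole trigger, PD status is undetermined by the text and may turn on the reporting unit or on how the sentence is read.

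The consequence is limited to exploratory TTP, DOR and PFS and to individual treatment stops for progression. The stated sample size, type I error and power are unaffected. How many subjects fall in the band, and whether the effect differs between sites, cannot be established from the protocol. The only assumption behind the calcium figures is the molar mass; the haemoglobin control rests on its own assumed constant.

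**What to change.** The sponsor should decide which level is meant and state one corrected-calcium threshold, with matching units, in both the Progressive Disease and Relapse rows of Appendix 1. As conversions, 11.5 mg/dL pairs with 2.87 mmol/L, and 2.65 mmol/L pairs with 10.6 mg/dL. This review does not choose between them. The creatinine unit in the same row can be corrected at the same time.

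Any PD called on calcium alone should then be checked against the single value; the protocol does not show whether any exist. The cost is a corrected figure in two rows and one check of calcium-based progression calls.

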16.2. Appendix 2: Revised Response Criteria for Malignant Lymphoma

Response Criteria for Malignant Lymphoma				
Response	Definition	Nodal Masses	Spleen, Liver	Bone Marrow
CR	Disappearance of all evidence of disease	(a). FDG-avid or PET positive prior to therapy; mass of any size permitted if PET negative (b). Variably FDG-avid or Pet negative; regression to normal size on CT	Not palpable, nodules disappeared	Infiltrate cleared on repeat biopsy; if indeterminate by morphology, immunohistochemistry should be negative
PR	Regression of measurable disease and no new sites	≥50% decrease in SPD of up to 6 largest dominant masses; no increase in size of other nodes (a). FDG-avid or PET positive prior to therapy; one or more PET positive at previously involved site (b). Variably FDG-avid or PET negative; regression on CT	≥50% decrease in SPD of nodules (for single nodule in greatest transverse diameter); no increase in size of liver or spleen	Irrelevant if positive prior to therapy; cell type should be specified
SD	Failure to attain CR/PR or PD	(a). FDG-avid or PET positive prior to therapy; PET positive at prior sites of disease and no new sites on CT or PET (b). Variably FDG-avid or PET negative; no change in size of previous lesions on CT		

Response Criteria for Malignant Lymphoma				
Response	Definition	Nodal Masses	Spleen, Liver	Bone Marrow
Relapsed Disease or PD	Any new lesion or increase by $\geq 50\%$ of previously involved sites from nadir	Appearance of a new lesion(s) > 1.5 cm in any axis, $\geq 50\%$ increase in SPD of more than one node, or $\geq 50\%$ increase in longest diameter of a previously identified node > 1 cm in short axis Lesions PET positive if FDG-avid lymphoma or Pet positive prior to therapy	$> 50\%$ increase from nadir in the SPD or any previous lesions	New or recurrent involvement

Abbreviations: CR = complete remission; FDG = [^{18}F]fluorodeoxyglucose; PET = positron emission tomography; CT = computed tomography; PR = partial remission; SPD = sum of the product of the diameters; SD = stable disease; PD = progressive disease

16.3. Appendix 4: NYHA Functional Classification System

The **New York Heart Association (NYHA) Functional Classification: Class I, II, III or IV Heart Failure** [NYHA, 1994] provides a simple way of classifying the extent of heart failure. It places subjects in one of 4 categories based on the level of limitation experienced during physical activity:

Class	Symptoms
Class I (Mild)	No limitation of physical activity. Ordinary physical activity does not cause undue fatigue, palpitation or dyspnea (shortness of breath).
Class II (Mild)	Slight limitation of physical activity. Comfortable at rest, but ordinary physical activity results in fatigue, palpitation or dyspnea.
Class III (Moderate)	Marked limitation of physical activity. Comfortable at rest, but less than ordinary physical activity results in fatigue, palpitation or dyspnea.
Class IV (Severe)	Unable to carry out any physical activity without discomfort. Symptoms of cardiac insufficiency at rest. If any physical activity is undertaken, discomfort is increased.

Reference:

The Criteria Committee of the New York Heart Association (NYHA). Nomenclature and Criteria for Diagnosis of Diseases of the Heart and Great Vessels. 9th Ed. Boston, Mass: Little, Brown & Co.; 1994:253-256.

16.4. Appendix 5: Modified Diet in Renal Disease Formula

MDRD	
$eGFR = 175 \times (S_{cr})^{-1.154} \times (Age)^{-0.203} \times (0.742 \text{ if female}) \times (1.212 \text{ if African American})$
 
GFR is expressed in mL/min/1.73 m², SCr is serum creatinine expressed in mg/dL, and age is expressed in years.
 
The link below will auto-calculate the creatinine clearance:
 
http://nephron.org/cgi-bin/MDRD_GFR/cgi

------	---

16.5. Appendix 6: ECOG Performance Status¹

Grade	Descriptions
0	Normal activity. Fully active, able to carry on all pre-disease performance without restriction.
1	Symptoms, but ambulatory. Restricted in physically strenuous activity, but ambulatory and able to carry out work of a light or sedentary nature (e.g. , light housework, office work).
2	In bed <50% of the time. Ambulatory and capable of all self-care, but unable to carry out any work activities. Up and about more than 50% of waking hours.
3	In bed >50% of the time. Capable of only limited self-care, confined to bed or chair more than 50% of waking hours.
4	100% bedridden. Completely disabled. Cannot carry on any self-care. Totally confined to bed or chair.
5	Dead.

1. [Oken, 1982]

Reference:

16.6. Appendix 7: Genetics

Genetics – Background

Naturally occurring genetic variation may contribute to inter-individual variability in response to medicines, as well as an individual's risk of developing specific diseases. Genetic factors associated with disease characteristics may also be associated with response to therapy, and could help to explain some clinical study outcomes. For example, genetic variants associated with age-related macular degeneration (AMD) are reported to account for much of the risk for the condition [Gorin, 2012] with certain variants reported to influence treatment response [Chen, 2012]. Thus, knowledge of the genetic etiology of disease may better inform understanding of disease and the development of medicines. Additionally, genetic variability may impact the pharmacokinetics (absorption, distribution, metabolism, and elimination), or pharmacodynamics (relationship between concentration and pharmacologic effects or the time course of pharmacologic effects) of a specific medicine and/or clinical outcomes (efficacy and/or safety) observed in a clinical study.

Genetic Research Objectives and Analyses

The objectives of the genetic research are to investigate the relationship between genetic variants and:

- Response to medicine, including GSK2857916 or any concomitant medicines;
- Multiple myeloma and lymphomas expressing BCMA susceptibility, severity, and progression and related conditions

Genetic data may be generated while the study is underway or following completion of the study. Genetic evaluations may include focused candidate gene approaches and/or examination of a large number of genetic variants throughout the genome (whole genome analyses). Genetic analyses will utilize data collected in the study and will be limited to understanding the objectives highlighted above. Analyses may be performed using data from multiple clinical studies to investigate these research objectives.

Appropriate descriptive and/or statistical analysis methods will be used. A detailed description of any planned analyses will be documented in a Reporting and Analysis Plan (RAP) prior to initiation of the analysis. Planned analyses and results of genetic investigations will be reported either as part of the clinical RAP and study report, or in a separate genetics RAP and report, as appropriate.

Study Population

Any subject who is enrolled in part 2 (expansion cohort) of the clinical study can participate in genetic research. Any subject who has received an allogeneic bone marrow transplant must be excluded from the genetic research.

Subject participation in the genetic research is voluntary and refusal to participate will not indicate withdrawal from the clinical study. Refusal to participate will involve no penalty or loss of benefits to which the subject would otherwise be entitled.

Study Assessments and Procedures

A key component of successful genetic research is the collection of samples during clinical studies. Collection of samples, even when no *a priori* hypothesis has been identified, may enable future genetic analyses to be conducted to help understand variability in disease and medicine response.

- A 6 ml blood sample will be taken for Deoxyribonucleic acid (DNA) extraction. A blood sample is collected at the baseline visit, after the subject has been randomized and provided informed consent for genetic research. Instructions for collection and shipping of the genetic sample are described in the laboratory manual. The DNA from the blood sample may undergo quality control analyses to confirm the integrity of the sample. If there are concerns regarding the quality of the sample, then the sample may be destroyed. The blood sample is taken on a single occasion unless a duplicate sample is required due to an inability to utilize the original sample.

The genetic sample is labelled (or “coded”) with the same study specific number used to label other samples and data in the study. This number can be traced or linked back to the subject by the investigator or site staff. Coded samples do not carry personal identifiers (such as name or social security number).

Samples will be stored securely and may be kept for up to 15 years after the last subject completes the study, or GSK may destroy the samples sooner. GSK or those working with GSK (for example, other researchers) will only use samples collected from the study for the purpose stated in this protocol and in the informed consent form. Samples may be used as part of the development of a companion diagnostic to support the GSK medicinal product.

Subjects can request their sample to be destroyed at any time.

Informed Consent

Subjects who do not wish to participate in the genetic research may still participate in the study. Genetic informed consent must be obtained prior to any blood being taken.

Subject Withdrawal from Study

If a subject who has consented to participate in genetic research withdraws from the clinical study for any reason other than being lost to follow-up, the subject will be given a choice of one of the following options concerning the genetic sample, if already collected:

- Continue to participate in the genetic research in which case the genetic DNA sample is retained
- Discontinue participation in the genetic research and destroy the genetic DNA sample

If a subject withdraws consent for genetic research or requests sample destruction for any reason, the investigator must complete the appropriate documentation to request sample destruction within the timeframe specified by GSK and maintain the documentation in the site study records.

Genotype data may be generated during the study or after completion of the study and may be analyzed during the study or stored for future analysis.

- If a subject withdraws consent for genetic research and genotype data has not been analyzed, it will not be analyzed or used for future research.
- Genetic data that has been analyzed at the time of withdrawn consent will continue to be stored and used, as appropriate.

Screen and Baseline Failures

If a sample for genetic research has been collected and it is determined that the subject does not meet the entry criteria for participation in the study, then the investigator should instruct the subject that their genetic sample will be destroyed. No forms are required to complete this process as it will be completed as part of the consent and sample reconciliation process. In this instance a sample destruction form will not be available to include in the site files.

Provision of Study Results and Confidentiality of Subject's Genetic Data

GSK may summarize the genetic research results in the clinical study report, or separately and may publish the results in scientific journals.

GSK may share genetic research data with other scientists to further scientific understanding in alignment with the informed consent. GSK does not inform the subject, family members, insurers, or employers of individual genotyping results that are not known to be relevant to the subject's medical care at the time of the study, unless required by law. This is due to the fact that the information generated from genetic studies is generally preliminary in nature, and therefore the significance and scientific validity of the results are undetermined. Further, data generated in a research laboratory may not meet regulatory requirements for inclusion in clinical care.

References

Gorin MB. Genetic insights into age-related macular degeneration: Controversies addressing risk, causality, and therapeutics. *Mol. Asp. Med.* 2012; 33: 467-486.

